**1.3                      Secondary Objectives**

Safety objectives

1.3.1      To evaluate the safety and tolerability of the combination of nivolumab plus ipilimumab.

Efficacy objectives:

- 1.3.2 To evaluate the objective response rate of the combination according to immune-related response criteria (irRC) [Wolchok *et al.*, 2009]. (Section 11).
- 1.3.3 To evaluate the Clinical Benefit Rate (CR + PR + SD  $\geq$  24 weeks) of the combination according to RECIST 1.1.
- 1.3.4 To evaluate the progression-free survival (PFS) of the combination according to RECIST 1.1.
- 1.3.5 To evaluate the Clinical Benefit Rate (CR + PR + SD  $\geq$  24 weeks) of the combination according to irRC [Wolchok *et al.*, 2009]. (Section 11).
- 1.3.6 To evaluate the progression-free survival (PFS) of the combination according to irRC [Wolchok *et al.*, 2009]. (Section 11)
- 1.3.7 To evaluate the objective response rate of the combination according to RECIST 1.1 in the population with centrally confirmed (via Foundation Medicine panel) hypermutated tumors ( $\geq$  9 mutations/megabase)
- 1.3.8 To evaluate the PFS of the combination according to RECIST 1.1 in the population with centrally confirmed hypermutated tumors ( $\geq$  9 mutations/megabase)
- 1.3.9 To evaluate the overall survival (OS) of the combination.

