High TMB is observed in approximately 2% of all breast cancers, and up to 3.5% in the metastatic setting (Barroso-Sousa et al, ASCO Annual Meeting 2018). Given that breast cancers are the most common malignancies in woman in the United States, this frequency represents a large number of individuals. Importantly, approximately 80% of these hypermutated tumors harbor an APOBEC mutational signature, and only approximately 18% have defective DNA mismatch repair (MMR) signature. Although pembrolizumab is approved for the treatment of MMR deficient tumors independently of cancer type, our data suggests that most hypermutated breast cancers would not be identified if using only the MMR status as a biomarker. Therefore, there is a critical need to evaluate if hypermutated tumors, independently of MMR status, are more likely to be responsive to immune checkpoint inhibitors.

Thus, we hypothesize that patients with hypermutated HER2-negative metastatic breast cancers are more likely to derive an objective response to the combination of nivolumab and ipilimumab. We propose to test this hypothesis by evaluating the combination of nivolumab 3mg/Kg every 2 weeks with ipilimumab 1mg/Kg every 6 weeks (1 cycle = 6 weeks) in patients with hypermutated metastatic HER2- breast cancer in an open-label, single arm phase II study. The primary endpoint will be to evaluate the efficacy of the nivolumab plus ipilimumab, as defined by objective response rate (ORR) according to RECIST 1.1 in patients with hypermutated HER2-metastatic breast cancer previously treated with 0 to 3 lines of systemic therapy in the metastatic setting. Additionally, we will perform correlative studies in order to explore the effect of treatment on immune-genomic markers in the peripheral blood and in the tumor microenvironment. Research biopsies will be performed at baseline (mandatory if the lesion is accessible) and at day 29 of Cycle 1 (+14 day scheduling window). Optional biopsies will be performed at progression in patients who experienced an objective response during the study. Moreover, blood samples will be collected within 7 days before starting therapy and every 6 weeks for 24 weeks, and then every 9 weeks. Furthermore, stool samples will be collected within 14 days before starting therapy and at day 29 of Cycle 1 (+14 day scheduling window).

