**Table 1: Regimen Description**

Agent	Premedication ; Precautions	Dose	Route	Schedule	Cycle Length
Nivolumab	Not routinely necessary unless prior infusion reaction.	3 mg/kg	IV over 60 minutes (+/- 5 minute infusion window)	Days 1, 15, 29	42 days (6 weeks)
Ipilimumab	Not necessary	1 mg/kg	IV over 60 minutes (+/- 5 minute infusion window)	Day 1	42 days (6 weeks)

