### 9. BIOMARKER, CORRELATIVE, AND SPECIAL STUDIES

In all patients in whom a tumor safely accessible, two biopsies will be required: baseline biopsy and on-treatment biopsy and at day 29 of cycle 1 (+14 day scheduling window). Optional biopsies will be performed at progression in patients who experienced an objective response during the study. We plan to use baseline biopsy tissue to perform a number of immune profiling assays, detailed below. On baseline tumor biopsies, we will perform characterization based on histology (TILs), protein expression, and mRNA expression. Additionally, we will bank specimens for possible future DNA analysis, and other further testing.

All participants will be asked to provide a sample of their archival tissue. For participants in whom tumor biopsies are not safely accessible, an archival sample will be required in order to enroll. In these cases, teams should ensure that an archival sample is available, but it does not need to be at the site in order for the patient to start treatment. Though listed as a screening procedure, archival tissue may be requested and obtained at any point throughout the trial.

Serial blood draws for correlative science are required on this trial; blood samples will be collected within 7 days before starting therapy; blood draws will be obtained every 6 weeks for 24 weeks, and then every 12 weeks, at the end-of-treatment visit in patients who are removed from treatment for progressive disease, and all efforts will be made to obtain an additional blood draw at the time of progressive disease, in patients who went off treatment for anything other than progressive disease. On each blood draw, we will perform flow cytometry to characterize protein expression of immune mediators, detailed below, and additional blood will be banked for future testing.

All patients will additionally be asked to provide a stool sample at three timepoints: within 14 days prior to starting treatment, during treatment at day 29 Cycle 1 (+14 day scheduling window), and at the end of treatment. A fourth collection may be requested from patients who experience grade  $\geq 2$  diarrhea related to study treatment after discussion with the PI. This collection is not required, but is strongly encouraged. These samples will be analyzed for microbiota content.

Sites may refer to the separate laboratory manual for additional correlative details including collection, processing, and shipping instructions.

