### 9.3 Blood Collection

Research blood collection is mandatory for all patients for flow cytometry and potential DNA isolation. The samples will be banked for these and future research purposes. These specimens will become the property of the DF/HCC.

The following research blood samples are required:

Baseline (preferably on Cycle 1 Day 1 prior to dosing):

- 1-10 mL Streck Tube for cfDNA
- 5-10mL CPT tubes for PBMCs

Every Restaging Visit (C2D1, C3D1, C4D1, C6D1, C8D1, etc.):

- 1-10mL Streck Tube for cfDNA
- 5-10mL CPT tubes for PBMCs

Off Treatment (if for progressive disease):

- 1-10 mL Streck Tube for cfDNA
- 5- 10mL CPT tubes for PBMCs

The following Time of Progression research blood samples are optional for patients who came off treatment for a reason other than progressive disease:

- 1-10 mL Streck Tube for cfDNA
- 5-10mL CPT tubes for PBMCs

For retreatment patients, research blood samples will be drawn with every restaging visit:

- 1-10 mL Streck Tube for cfDNA
- 5-10mL CPT tubes for PBMCs

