### 10. STUDY CALENDAR

Screening evaluations are to be conducted within 28 days prior to start of protocol therapy unless otherwise specified. Screening assessments occurring within 4 days prior to initiating study treatment do not need to be repeated on Cycle 1 Day 1.

As detailed in the Study Calendar, laboratory assessments including a negative pregnancy test in women of child-bearing potential must be documented within 7 days before the first dose of study medication.

In the event that the participant's condition is deteriorating, laboratory evaluations should be repeated within 48 hours prior to initiation of the next cycle of therapy.

Assessments must be performed prior to administration of any study agent. Study assessments and agents should be administered within  $\pm$  3 days of the protocol-specified date, unless otherwise noted.

	Screening a	Cycle 1			Cycle 2-4			Cycle 5+			End of Treatment q	Follow-Up
		Day 1	Day 15	Day 29	Day 1	Day 15	Day 29	Day 1	Day 15	Day 29		
Medical History b	X											
Physical exam c	X	X	X	X	X			X			X	
Concurrent medications d	X	X			X			X			X	
ECOG	X	X			X			X			X	
Adverse event evaluation		X	X	X	X	X	X	X	X	X	X s	
Vital signs c	X	X	X	X	X	X	X	X	X	X	X	
Hematology panel f	X	X	X	X	X	X	X	X	X	X	X	
Chemistry panel g	X	X	X	X	X	X	X	X	X	X	X	
Urine Protein Creatinine Ratio	X				X			X			X	
TSH/ft4	X	X			X			X h			X	
ACTH/Cortisol	X	X			X			X h				
Amylase and Lipase	X	X			X			X h				
Coagulation panel (PT/PTT)	X											
Pregnancy test i	X i	X i		X i	X i	X i	X i	X i	X i	X i		
12- lead EKG	X											
Tumor Assessment j	X				X			X			X k	X k
Research Blood l		X			X			X			X	X
Research Biopsy m	X			X							X	
Archival Tumor Retrieval n	X											
Quality of Life r	X				X			X				
Research Stool Collection & Questionnaire o, p (Section 9.4)	X			X							X	
Survival (Section 5.6)												X

- a. Screening assessments are to be conducted within 28 days prior to start of protocol therapy unless otherwise specified. If these screening assessments occur within 4 days before start of study treatment, then they may serve as the baseline Cycle 1 Day 1 values.

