- j. Tumor assessments should consist of 1) CT and/or MRI of the chest/abdomen/pelvis, 3) any other imaging studies (CT neck, plain films, etc.) as clinically indicated by the treating physician. The same radiographic procedures and technique must be used throughout the study for each patient (e.g., if the patient had CT chest/abdomen/pelvis performed during screening, then she should subsequently undergo CT performed using the same radiologic protocol throughout the remainder of the study). Tumor assessments will be performed at baseline, at day 1 ( $\pm 7$  day scheduling window) of Cycles 2, 3, and 4 and then every 12 week [ at day 1 ( $\pm 7$  day scheduling window) of every odd cycle: C6, C8, C10, etc.]. Additional scans are permitted as clinically indicated. All known sites of disease documented at screening should be re-assessed at each subsequent tumor evaluation.
- k. For those taken off the study for reasons other than progressive disease, tumor measurements should continue to be repeated every 6-12 weeks until first disease progression or start of a new anti-cancer therapy. Every effort should be made to maintain this scheduled, but it is understood that it may not be possible in all cases. Failure to complete scans at this interval will not be deemed protocol violations.
- l. Collected at screening, every restaging, end of treatment (if removed for progressive disease) and optionally at time of progression. See section 9.0
- m. Baseline tumor biopsy should be obtained within 28 days prior to initiating protocol therapy. On treatment biopsies should be obtained at C1D29 (+14 day scheduling window). A tumor biopsy may be performed at the end of treatment. See Section 9.2.
- n. Archival tumor sample should be collected (block or if not possible, 10-20 5micron, unstained positively charged slides). This sample may be collected at any time throughout the lifetime of the study.
- o. Baseline stool collection should be obtained within 14 days before starting protocol therapy. On treatment stool collection should be obtained at C1D29 (anytime from C1D29-C2D1). A stool collection should be obtained at the end of treatment. As these collections are for exploratory correlative purposes, failure to provide a sample at these timepoints will not constitute a protocol violation. See section 9 and/or lab manual for stool collection and processing instructions.

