## 11. MEASUREMENT OF EFFECT

For the purposes of this study, participants should be re-evaluated for response approximately every 6 weeks for the first 24 weeks and then every 12 weeks thereafter. If cycles are delayed for any reason, the scan schedule should be moved to align with cycles of treatment received.

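### Footnote j's scan list (C6, C8, C10) contradicts Section 11 and leaves no scheduled scan near week 24, so the clinical benefit rate is biased upward under the 11.1.4 dating rule

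*Combined protocol and SAP*

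**What the plan says.** The Study Calendar row "Tumor Assessment" marks day 1 of Cycles 2-4 and of Cycle 5+, and leaves the cycle numbers after C4 to footnote j. That footnote schedules scans at C2, C3 and C4, then 12-weekly on day 1 "of every odd cycle: C6, C8, C10, etc", with a window of 7 days either side. It allows extra scans when clinically indicated.

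Section 9.3 repeats the even-numbered list for research blood: "Every Restaging Visit (C2D1, C3D1, C4D1, C6D1, C8D1, etc".

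Section 11 says "participants should be re-evaluated for response approximately every 6 weeks for the first 24 weeks and then every 12 weeks thereafter". The introduction to Section 9 follows that second pattern: "blood draws will be obtained every 6 weeks for 24 weeks, and then every 12 weeks".

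Clinical benefit is a secondary endpoint (1.3.3, 1.3.5, 11.1.5, 13.4). It counts CR, PR, or stable disease (SD) lasting at least 24 weeks. Section 11.1.4 measures SD from the start of treatment until progression criteria are met. Section 11.3 gives no duration rule for irSD.

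**The concern.** Footnote j contradicts itself, because C6, C8 and C10 are not odd cycles. Its list also contradicts Section 11. In a multicenter trial, sites could follow different scan schedules and each claim to comply.

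The visit the list leaves out is C5D1, which is day 168 after C1D1, exactly 24 weeks. That is the threshold the SD component of clinical benefit depends on. A patient stable at week 18 who progresses at week 20 would, without an unscheduled scan, first be seen to progress at about week 30. Under 11.1.4 as written, that patient is credited with some 30 weeks of SD and counted as a clinical benefit. Progression dates for PFS move with the schedule in the same way.

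**Working it through.** **Calendar.** Table 1 gives 42-day cycles, so week of CkD1 = (k - 1) x 42 / 7, plus or minus 1 week.

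| Source | Cycles | Weeks |
|---|---|---|
| Footnote j list (9.3 agrees through C8) | C2, C3, C4, C6, C8, C10 | 6, 12, 18, 30, 42, 54 |
| Section 11 | C2, C3, C4, C5, C7, C9 | 6, 12, 18, 24, 36, 48 |

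Only the word odd in footnote j reproduces Section 11; the listed cycle numbers do not. Under the list the C4 window is weeks 17-19 and the C6 window is weeks 29-31, so nothing is scheduled from week 19 to week 29.

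**Who is left unresolved under the list.**
- PD by the week-18 scan: SD of 24 weeks is ruled out.
- Non-PD at the week-30 scan: SD of 24 weeks is established.
- CR or PR: counted regardless of duration.
- No CR or PR, and first PD at C6 or assessment ended between C4 and C6: 24-week status is interval-censored between weeks 18 and 30, unless an unscheduled or end-of-treatment scan fills the gap.

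**Size (illustration only).** Assume exponential time to progression, S(t) = 0.5^(t / median), with medians of 12, 17.4 and 31.3 weeks. The documents give no expected median for this population.

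*With the footnote list*, the literal 11.1.4 rule credits everyone not progressed at week 18. The true rate is S(24), so the bias is S(18) - S(24).

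*With a C5D1 scan spread evenly over plus or minus 7 days*, half the scans fall on or after day 168, and PD first seen there still counts as 24 weeks. The other half fall at about week 23.5 on average, and PD seen there does not count. The literal rate is about 0.5 x S(18) + 0.5 x S(23.5), with S(23.5) = 0.257, 0.392 and 0.594. That gives about 0.306, 0.440 and 0.633, in line with a simulation of 1,000,000 patients per median (0.305, 0.440, 0.633).

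| Median (weeks) | S(18) | S(24) | Bias, list | Bias, C5D1 scan | Added by the list | Of 30 patients |
|---|---|---|---|---|---|---|
| 12 | 0.354 | 0.250 | +0.104 | +0.055 | 0.049 | 1.5 |
| 17.4 | 0.488 | 0.384 | +0.104 | +0.056 | 0.048 | 1.4 |
| 31.3 | 0.671 | 0.588 | +0.084 | +0.046 | 0.038 | 1.1 |

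(Differences come from unrounded values.)

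Responders cannot be misclassified this way. Taking the responder share as 5% to 25%, the two rates in Section 13.2, the list's contribution becomes 0.038 x 0.75 = 0.029 to 0.049 x 0.95 = 0.047, about 0.9 to 1.4 patients. Unscheduled scans that catch progression early reduce it further.

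**A visit-based rule.** If SD of 24 weeks instead requires a non-PD result at the C5D1 visit, the simulated rates are 0.250, 0.385 and 0.588 against true values of 0.250, 0.384 and 0.588, a bias within 0.1 point. This assumes every patient attends within the window.

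**Scale.** One patient is 1/30 = 3.3 points. A result of 12/30 has a 95% exact interval of 23% to 59%.

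**The case against.** The best defense is that the even list is deliberate and odd is a slip for other. Footnote h moves laboratory tests to every other cycle after Cycle 4, and footnote r puts quality of life at C6D1 and C8D1, as 9.3 does for blood. Four cycles last 24 weeks, and Section 11 says only approximately, so one could argue that scans at C2 to C4 followed by 12-weekly scans satisfy it. This may explain where the list came from, and it makes it more likely that sites follow it. It does not remove the conflict: a 12-week gap that opens at week 18 is not 6-weekly assessment through week 24. Even if the list were intended, no scan would fall near the 24-week threshold.

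Three other objections stand and limit the point.
- A reader might infer that SD of at least 24 weeks cannot be determined at all. The documents do not support that. The week-18 and week-30 scans settle most patients, and 11.1.4 assigns a duration even to those with PD at week 30. The fault is bias in that group.
- A reader might attribute the whole 8 to 10 points to the list. About half comes from the 11.1.4 dating rule and would remain with a C5D1 scan.
- A reader might fear that the rate could equally be understated. That needs a convention requiring a non-PD scan on or after week 24, which the documents do not contain for RECIST clinical benefit.

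**Conclusion.** The inconsistency is real and rests on the text alone: footnote j and 9.3 cannot be followed together with Section 11. If sites follow the list, no scheduled scan falls at or near week 24, and 11.1.4 as written biases the RECIST clinical benefit rate upward. For clinical benefit by irRC the direction is open, because no irSD duration rule is given.

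Under the assumed exponential medians, the literal rule overstates the rate by up to 8 to 10 points with the list and about 5 to 6 points with a C5D1 scan. The list itself therefore accounts for about 4 to 5 points, or 1.1 to 1.5 of 30 patients, before allowing for responders and early detection. That is well inside sampling error at this sample size, but it is systematic and avoidable.

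PFS dates also depend on which schedule a site uses. It would be tempting to extend the point to the primary endpoint, but no effect on ORR or the two-stage rule has been shown. The point concerns secondary, descriptive endpoints and should be corrected on that footing.

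**What to change.** 1. Reconcile footnote j and Section 9.3 with Section 11, so that one schedule applies at all sites and includes the week-24 (C5D1) assessment that Section 11 already calls for. Check footnote l (blood at each restaging) and footnote r (quality of life at C6D1, C8D1) for consistency. Scans also inform stopping for progression (5.5), so the clinical side of the schedule is for the sponsor and investigators; the statistical need is a common schedule with an assessment at week 24.

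2. Fixing the cycle numbers alone leaves the 11.1.4 problem, so add to 11.1.5 and 13.4: *SD of at least 24 weeks requires a non-PD assessment at the week-24 visit (C5D1, +/-7 days) or, if that scan is missed, at a later scan with no intervening PD; PD first documented at the week-24 visit does not count.* The fallback keeps a patient who missed C5D1 but was still stable later. State whether the same rule applies to irSD.

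The cost is wording, plus one scan at week 24 for patients still under assessment. Later scans come 6 weeks earlier at the same 12-week interval, so both schedules have six on-treatment scans through week 54. Restaging blood moves with the scans; quality of life would no longer coincide with them unless footnote r is aligned.

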## 1.5 Patient Reported Outcomes Objectives

- 1.5.1 To assess the participant's quality of life by the FACT-B questionnaire
- 1.5.2 To assess the participant's quality of life by the Rotterdam Symptom Checklist

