## 6.2 Dose Delays

Dosing of ipilimumab or nivolumab may be held at the treating investigator’s discretion for any toxicity of any grade. Additionally, holding of the study agents may be required as indicated in the tables in **Section 6.1**.

A treatment delay of up to six weeks for nivolumab and up to 12 weeks for ipilimumab is allowable. Participants requiring a longer hold should be removed from protocol therapy. Exceptions for participants exhibiting clinical benefit may be possible with approval from the principal investigator.

If study agent dosing is held due to toxicity, the counting of cycle days and assessment schedule will continue without interruption. For example, a participant who does not receive their Cycle 3 Day 15 dose of nivolumab due to toxicity will proceed with their next regularly scheduled clinic visit (Cycle 3 Day 29) as previously planned. Alternatively, if ipilimumab is held on C3D1 and nivolumab is given, the ipilimumab dose would be omitted for that cycle. Additional interim clinic visits may be scheduled to manage toxicity, however the cycle will not restart due to dosing delays due to adverse events and the assessment schedule (including tumor imaging evaluations) will continue as originally planned.

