- p. An optional stool sample may be collected at the time of grade  $\geq 2$  diarrhea after discussion with the PI. As these collections are for exploratory correlative purposes, failure to provide a sample or complete the stool questionnaires at these timepoints will not constitute a protocol violation. See section 9 and/or lab manual for stool collection and processing instructions.
- q. End of treatment visit is to occur within 30 days of final administration of study treatment. End of treatment assessments do not have to be repeated if the same assessments were performed within 7 days (28 days for tumor assessments) prior to the visit.

- r. FACT B and the Rotterdam Symptom Checklist should be completed baseline or C1D1 (any time prior to first dose), D1 of C2-C4, and then on D1 of every other cycle (C6D1, C8D1, etc.) These questionnaires may be found in Appendices C and D.
- s. An adverse event assessment is performed 100 days (-15/+30 days) after the last dose of nivolumab. This may be conducted in person or by phone by the investigator or suitably trained and qualified delegate (i.e. MD, RN, NP, etc).

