#### 11.3.1.6 Patient Reported Outcome Assessments

The PRO outcome measure for this study is as follows: Scores from the FACT-B assessment (Appendix C) and Rotterdam Symptom Checklist (Appendix D).

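### FACT-B and the Rotterdam checklist are left off the existing end-of-treatment visit, so patients who leave therapy between scheduled Day 1 visits give no quality-of-life score at stopping

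*Combined protocol and SAP*

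**What the plan says.** Section 1.5 sets two patient-reported objectives, one per instrument. The first reads "To assess the participant's quality of life by the FACT-B questionnaire". Section 11.3.1.6 defines the outcome as "Scores from the FACT-B assessment (Appendix C) and Rotterdam Symptom Checklist (Appendix D") and gives no time points.

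The time points are in Section 10. Footnote r says "FACT B and the Rotterdam Symptom Checklist should be completed baseline or C1D1 (any time prior to first dose), D1 of C2-C4". After cycle 4 the forms move to alternate cycles, starting with cycle 6. The quality-of-life row of the grid matches: it is marked at Screening, at Day 1 of cycles 2-4 and at Day 1 of cycle 5 onward, and it is blank under End of Treatment and Follow-Up.

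Footnote q provides the visit that the row omits: "End of treatment visit is to occur within 30 days of final administration of study treatment". Physical examination, ECOG, adverse events, vital signs, laboratory tests, tumor assessment, research blood, biopsy and stool are all marked there. For stool, footnote o says "A stool collection should be obtained at the end of treatment", and that row carries its own questionnaire.

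No other section adds a later form. Section 5.6 follows adverse events, first progression and survival. Section 13 contains no quality-of-life analysis and no method for missing scores.

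**The concern.** Every form after baseline is tied to a Day 1 visit on protocol therapy. Patients who leave therapy between those visits, notably for toxicity or progression, are not asked how they are when they stop. Both reasons are plausibly linked to quality of life, so the scores that remain come from a selected group.

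If summaries for objectives 1.5.1 and 1.5.2 use only the scores in hand, later means rest on those who stayed. A flat or rising curve could then reflect who is left rather than how patients fared. A score at stopping cannot be recovered afterwards, so the gap has to be closed in the schedule and not in the analysis.

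**Working it through.** **Inputs.** Cycle length 6 weeks (Section 1.1). Questionnaire schedule (Section 10, footnote r). End-of-treatment visit within 30 days of last dose (footnote q). Target of 30 evaluable patients (Section 13.1). The plan states no sample size, power or expected completion for quality of life, so there is no figure of its own to reproduce.

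**Step 1: place the forms in time.** Week of Day 1 = 6 × (cycle − 1).
- C2: 6 × 1 = 6
- C3: 6 × 2 = 12
- C4: 6 × 3 = 18
- C6: 6 × 5 = 30
- C8: 6 × 7 = 42

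The gaps are 12 − 6 = 6 and 18 − 12 = 6 weeks, then 30 − 18 = 12 and 42 − 30 = 12 weeks.

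**Step 2: what a leaver contributes.**
- Leaves in cycle 1, before C2D1: baseline only.
- Leaves in cycle 2: one later score, at week 6.
- Leaves in cycle 3: two, at weeks 6 and 12.
- Leaves between C4D1 and C6D1: three, the last up to about 12 weeks old.

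Visit windows shift these by a few days.

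**Step 3: how many patients this could touch (illustration).** The documents give no expected time on therapy. Assume exponential time on therapy with median m weeks (months × 365.25 / 12 / 7). The expected number still on therapy at week w is 30 × 0.5^(w/m).

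| Assumed median | Week 6 | Week 12 | Week 18 | Week 30 |
|---|---|---|---|---|
| 2 months | 18.6 | 11.5 | 7.1 | 2.7 |
| 4 months | 23.6 | 18.6 | 14.6 | 9.1 |
| 6 months | 25.6 | 21.8 | 18.6 | 13.5 |
| 8 months | 26.6 | 23.6 | 21.0 | 16.5 |

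By week 18, between 30 − 21.0 = 9.0 and 30 − 7.1 = 22.9 patients have left, roughly 9 to 23 of 30. None has a form scheduled after leaving. As context only, Section 2.5.3.1 reports that 17.4% of patients on this regimen in a lung cancer trial discontinued for treatment-related adverse events. On 30 patients that would be 0.174 × 30 = 5.2.

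**Step 4: direction.** Section 5.5 allows stopping for confirmed complete response only after at least 24 weeks, and otherwise caps treatment at 24 months. Neither route can remove a patient before the week-18 form. Leaving by then is for progression, toxicity, intercurrent illness, non-compliance, withdrawal or investigator judgment. That makes favorable selection the likelier direction early on. From week 30 the complete-response route can pull the other way.

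**Step 5: what an end-of-treatment form would add.** Take a patient whose last dose is cycle 1 Day 15 (2 weeks in) and who then leaves therapy. The visit falls by about 2 + 30/7 = 6.3 weeks. The patient would have one post-baseline score instead of none, but still no score at weeks 12 or 18.

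**The case against.** The strongest reply is that the schedule is less selective than it looks.

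- A reader might infer that quality of life is seen only in patients well enough to start another cycle. The documents do not support that. Baseline is scheduled for everyone. Section 6.2 says "If study agent dosing is held due to toxicity, the counting of cycle days and assessment schedule will continue without interruption", so a patient too unwell to be dosed can still reach a form. Section 5.5 also lets patients stay on therapy past RECIST progression. The accurate condition is being on protocol therapy at a scheduled Day 1.
- The forms fall at the same visits as tumor assessment (footnote j), so a patient whose progression is found at scheduled restaging may complete one at about that time. This stands in part. The scan window of ±7 days means it is not assured, and it does not help with mid-cycle stopping for toxicity.
- Patients who stop for complete response or at 24 months also give no later form, unless a complete responder enters the retreatment phase. This stands, and it means the loss is not confined to patients who worsen.
- A reader might infer that no model could correct the loss. That is too absolute: a likelihood-based mixed model uses earlier scores and is valid if dropout depends only on what was observed. The narrower point survives, that without scores near stopping this assumption is hard to examine.
- On-treatment quality of life is a legitimate descriptive target, and ECOG and adverse events are recorded at end of treatment. Both are true, but neither replaces the patient's own report.

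**Conclusion.** The point holds as a minor, inexpensive improvement. Footnote r and the grid agree that neither questionnaire is given at end of treatment, and no other section supplies one. Patients leaving between scheduled visits give no score at stopping: nothing after baseline in cycle 1, and otherwise a last score up to about 6 weeks old through C4D1 or about 12 weeks old later. On-treatment summaries are open to selection, probably favorable on balance; that direction is a judgment resting on Step 4.

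The size of the bias cannot be estimated from the documents. A reader might be tempted to put a number on it. If half the patients had stopped by week 12 and would score 10 FACT-B points lower than those continuing, the observed mean would be 0.5 × 10 = 5 points too high; with 30% to 70% stopped, 3 to 7 points. The arithmetic is right, but the 10-point difference is an assumption and is held fixed across that range. The plan nowhere states an all-patient week-12 mean as its target, and the proposed form would not fully supply that mean. These figures should not be read as an estimate.

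Quality of life is a separate patient-reported objective in a single-arm trial, and no decision rule in Section 13 depends on it.

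**What to change.** Mark both questionnaires in the End of Treatment column of the calendar, and add the visit to footnote r. In Section 13, state that the end-of-treatment score enters the change-from-baseline summary or mixed model. Place it at its actual time since first dose, because it falls at a different week for each patient. Report the number of forms expected and completed at each visit, by reason for leaving therapy.

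The cost is a calendar amendment and one extra form set at a visit patients already attend. Footnote q already waives end-of-treatment assessments done within the preceding 7 days, so some patients would not need to repeat the forms. The amendment is worth making early, since scores at stopping cannot be collected in retrospect. It reduces the gap but leaves quality of life after the end-of-treatment visit unobserved, and the report should say so.
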